10.1.7 Source Documents

- Source documents provide evidence for the existence of the participant and substantiate the integrity of the data collected. Source documents are filed at the Investigator's site.
- The Investigator is responsible for the quality of the data recorded in the CRFs. The data recorded should be a complete and accurate account of the participant's record collected during the study.
- Data reported on the CRF or entered in the electronic CRF that are transcribed from source documents must be consistent with the source documents or the discrepancies must be explained. The Investigator may need to request previous medical records or transfer records, depending on the study. Also, current medical records must be available.
- Source documents may be electronic, hard copy, or a combination of both and are defined as the results of original observations and activities of a clinical investigation. When using a direct entry CRF, the CRF will be considered the source document for applicable CRF elements collected directly onto a CRF. Source documents will include, but are not limited to, progress notes, electronic data, screening logs, and recorded data from automated instruments. Source documents will include, but are not limited to, progress notes, electronic data, screening logs, and recorded data from automated instruments pertaining to this study will be maintained by the Investigator and made available for direct inspection by the authorised study personnel outlined in the ICF.
- The Investigator must maintain accurate documentation (source data) that supports the information entered in the CRF.
- Indivior or designee will perform monitoring to confirm that data entered into the CRF by authorised site personnel are accurate, complete, and verifiable from source documents; that the safety and rights of participants are being protected; and that the study is being conducted in accordance with the currently approved protocol and any other study agreements, ICH GCP, and all applicable regulatory requirements.

10.1.8 Study and Site Start and Closure

First Act of Recruitment

The study start date is the date on which the clinical study will be open for recruitment of participants.

The first act of recruitment is the time study is published to the call centre and Helpresearch.com website and will be the study start date.

Study/Site Termination

Indivior or designee reserves the right to close the study site or terminate the study at any time for any reason at the sole discretion of Indivior. Study sites will be closed upon study

completion. A study site is considered closed when all required documents and study supplies have been collected and a study-site closure visit has been performed.

The Investigator may initiate study-site closure at any time, provided there is reasonable cause and sufficient notice is given in advance of the intended termination.

Reasons for the early closure of a study site by Indivior or Investigator may include but are not limited to the following:

For study termination:

• Discontinuation of further study drug development

For site termination:

- Failure of the Investigator to comply with the protocol, the requirements of the IRB/IEC or local health authorities, Indivior procedures, or GCP guidelines
- Inadequate or no recruitment (evaluated after a reasonable amount of time) of participants by the Investigator
- Total number of participants included earlier than expected

If the study is prematurely terminated or suspended, Indivior shall promptly inform the Investigators, the IRBs/IECs, the regulatory authorities, and any contract research organisation(s) used in the study of the reason for termination or suspension, as specified by the applicable regulatory requirements. The Investigator shall promptly inform the participant and should assure appropriate participant therapy and/or follow-up.

10.1.9 Publication Policy

The study data will be owned by Indivior. Publication of any and all data will be at the discretion of Indivior. The Investigator will not disseminate, present, or publish any of the study data without the prior written approval from Indivior to do so.

Indivior will comply with the requirements for publication of study results. In accordance with standard editorial and ethical practice, Indivior will generally support publication of multicentre studies only in their entirety and not as individual site data. In this case, a coordinating Investigator will be designated by mutual agreement. Authorship will be determined by mutual agreement and in line with International Committee of Medical Journal Editors authorship requirements.

10.2 Appendix 2: Clinical Laboratory Tests

- The tests detailed in Table 5 will be performed by the local laboratory.
- Protocol-specific requirements for inclusion or exclusion of participants are detailed in Section 5.
- Additional tests may be performed at any time during the study as determined necessary by the Investigator or required by local regulations.

Table 5 Protocol-required Safety Laboratory Tests

Haematology	Serum Chemistry *		
Haemoglobin	Blood Urea Nitrogen		
Haematocrit	Bilirubin (total and direct)		
Total and differential leukocyte count	ALP		
Red blood cell count	AST		
Platelet count	ALT		
	Gamma-glutamyl Transferase		

Coagulation

Prothrombin time/INR Activated partial thromboplastin

Urinalysis

pH Specific gravity Protein *** Glucose Ketones Bilirubin Blood *** Nitrite*** Urobilinogen Leukocyte esterase ***

Blood Urea Nitrogen Bilirubin (total and direct) ALP AST ALT Gamma-glutamyl Transferase Albumin Sodium Potassium Chloride Glucose (fasting) Creatinine ** Total protein Total cholesterol Triglycerides Creatine phosphokinase

Additional Tests

HIV-1; HIV-2 (screening only) HBsAg (screening only) HCV antibodies (screening only) Urine drug screen

- Opiates
- Opioids
- Amphetamines
- Barbiturates
- Benzodiazepines
- Cocaine
- Cannabinoids
- Fentanyl
- Oxycodone
- Urine alcohol screen
- COVID-19 rapid test (check-in only)
- * Serum chemistry tests will be performed after at least an 12-hour fast; however, in case of dropouts or rechecks, participants may not have fasted for 12 hours prior to when the serum chemistry sample is taken.
- ** At the Screening Visit, creatinine clearance will be calculated using the Cockcroft-Gault formula.
- *** If urinalysis is abnormal for protein, blood, nitrite and/or leukocyte esterase, a microscopic examination (for red blood cells, white blood cells, bacteria, casts, and epithelial cells) will be performed.

10.3 Appendix 3: Contraceptive Guidance and Collection of Pregnancy Information

10.3.1 Contraception Guidance

Male Participants

Male participants with female partners of childbearing potential must comply with the following contraception requirements from the time of dosing of study drug until at least 90 days after dosing of study drug.

- All non-sterile male participants must use highly effective contraception from study drug administration through 90 days after study drug administration if sexually active with a non-pregnant partner of child bearing potential. Highly effective contraception is defined as:
 - o True sexual abstinence
 - o Condom plus partner's use one of the following:
 - Oral, intravaginal, injectables, implants, or transdermal combined (estrogen- and progestogen-containing) hormonal contraception associated with inhibition of ovulation
 - □ Intrauterine device
 - □ Intrauterine hormone-releasing system
 - Bilateral tubal occlusion
- No restrictions are required for a vasectomised male provided his vasectomy has been performed 4 months or more prior to dosing. A male who has been vasectomised less than 4 months prior to dosing must follow the same restrictions as a non-vasectomised male.
- Male participant must agree not to donate sperm from dosing until at least 90 days post-dose.

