4.1.1 Discharge Criteria

All urine and fecal collections will be analysed for radioactivity levels to determine if a discharge criterion is met. Participants will be confined to the study site until at least Day 8. Participants will be discharged from the study site on Day 8 if one of the following discharge criteria is met:

 \geq 90% of the total dose of radioactivity administered has been recovered in urine and feces;

OR

There is $\leq 1\%$ of the total administered radioactivity in each of 2 consecutive 24-hour intervals where both a urine and fecal sample is provided.

If neither discharge criterion is met by Day 8, participants will remain confined until at least one discharge criterion is met or up to a maximum stay of 21 days post-dose (ie, Day 22).

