5.1 Inclusion Criteria

Participants are eligible to be included in the study only if all of the following criteria apply:

- 1. Participant must be 19 to 55 years of age inclusive, at the time of signing the informed consent.
- 2. Participant must have body weight of a minimum of 50.0 kg at the Screening Visit and body mass index within the range 18.0 to 32.0 kg/m² (inclusive).
- 3. Participant must be male and who is healthy as determined by medical evaluation.
- 4. Participant agrees to follow contraception guidelines in Section 10.3 (Appendix 3).
- 5. Participant must be continuous non-smoker who has not used nicotine- and tobacco-containing products for at least 3 months prior to dosing based on participant self-reporting.
- 6. Participant must be capable of giving signed informed consent as described in Section 10.1.3 (Appendix 1) which includes compliance with the requirements and restrictions listed in the ICF and in this protocol.

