7.2 Participant Discontinuation/Withdrawal From the Study

- A participant may withdraw from the study at any time at the participant's own request for any reason (with or without providing any reason).
- A participant may be withdrawn at any time at the discretion of the Investigator for safety, behavioural or compliance reasons.
- At the time of discontinuing from the study, if possible, discharge assessments should be conducted, as shown in the SoE (Section 1.3).
- Participants who terminate the study early will be asked to return to the study site 7±2 days after dosing for follow-up procedures, and to determine if any AE has occurred since the last study visit, as shown in the SoE (Section 1.3).
- The participant will be permanently discontinued both from the study drug and from the study at that time.
- The participant will be encouraged to stay up to 24 hours post-dose to complete discharge assessments.
- If the participant withdraws consent for disclosure of future information, Indivior may retain and continue to use any data collected before such a withdrawal of consent.
- If a participant withdraws from the study, the participant may request destruction of any samples taken and not tested, and the Investigator must document this in the site study records.

Should any participant withdraw or be withdrawn from the study, they will be cautioned against activities requiring mental alertness, judgment and physical coordination such as driving, operating machinery, or power equipment for a period of 24 hours post-dose.

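### Minor: protocol Section 10.3.1 sets no precaution for a man whose partner is already pregnant, although Section 8.4.5 follows possible foetal exposure through semen

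*Protocol*

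**What the plan says.** Protocol Section 10.3.1 contains three rules for the 90 days after dosing.

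- Non-sterile men must practise true abstinence, or use a condom together with a listed partner method, "if sexually active with a non-pregnant partner of child bearing potential".
- Men vasectomised 4 months or more before dosing have no restriction. Those vasectomised more recently are treated like men without a vasectomy.
- No participant may donate sperm.

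Two inclusion criteria in Section 5.1 make rules of this kind binding. Criterion 4 reads "Participant agrees to follow contraception guidelines in Section 10.3 (Appendix 3"), and so adds nothing beyond that appendix. Criterion 6 requires consent that includes "compliance with the requirements and restrictions listed in the ICF and in this protocol".

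Section 8.4.5 collects partner pregnancies from dosing until 90 days afterwards. It follows to outcome those in which an embryo or foetus may have been exposed, and it gives passage of a medicinal product in semen as the route.

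**The concern.** The operative bullet of Section 10.3.1 takes pregnant partners out of the condom or abstinence duty by its own wording. The vasectomy bullet lifts the duty whatever the partner's status. If the only aim is to prevent conception, both exclusions make sense. If drug in semen is also a possible route to a foetus, which is how Section 8.4.5 frames its follow-up cases, then a pregnancy already under way is a case where a precaution could matter, and a vasectomy gives no evident protection against it.

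What would be at stake is an avoidable, possible exposure of a third party who gains nothing from the study. Section 2.3.2 states that participants themselves receive no direct health benefit from the drug. The mass balance, pharmacokinetic and adverse event analyses are not touched.

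**Working it through.** There is no figure in the plan to reproduce. The check sets the texts side by side.

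**1. What Section 10.3.1 requires, by man and partner**

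| Man | Partner not pregnant, of childbearing potential | Partner already pregnant |
|---|---|---|
| No vasectomy, or one less than 4 months before dosing | Abstinence, or condom plus partner method, to 90 days | Nothing stated |
| Vasectomy 4 months or more before dosing | Nothing required | Nothing required |

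The section's opening sentence speaks more broadly of female partners of childbearing potential. It only directs men to the requirements that follow, so it does not bring pregnant partners back in. The sperm donation ban does not address intercourse.

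**2. Whether another readable section fills the right-hand column**

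- Section 5.1: criterion 4 points back to Section 10.3. Criterion 6 points to the protocol and the consent form. The consent form is not shown.
- Section 5.2: no exclusion mentions a pregnant partner.
- Section 5.3: the lifestyle rules cover diet, caffeine, alcohol, tobacco and activity only.
- Section 7.2: men who withdraw are cautioned about driving and machinery for 24 hours after dosing. Pregnant partners are not mentioned.

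None does so in the readable text.

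**3. What Section 8.4.5 adds**

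It governs reporting and follow-up, not prevention. It does not say expressly whether a pregnancy already present at dosing counts.

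**4. How far confinement helps**

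- Inputs: the 90-day window (Section 10.3.1); earliest discharge on Day 8, which is 7 days after dosing; latest on Day 22, which is 21 days after dosing (Section 4.1.1).
- Days of the protocol's own window spent outside the unit: 90 − 7 = 83 at most and 90 − 21 = 69 at least, for men who stay to discharge. Both are approximate, because release may lag a criterion by about a day.
- These are counts of days, not a measure of exposure. Any drug left would be falling throughout.
- Confinement does not bind a man who leaves early. Section 7.2 states "A participant may withdraw from the study at any time", and "The participant will be encouraged to stay up to 24 hours post-dose to complete discharge assessments" is encouragement only. Section 9.5 allows for at most 1 such man among 7.

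**The case against.** The strongest reply is that the answer may lie in material not shown. The consent pages were removed, the study-drug risk text in Section 2.3.1 is blank, and Section 2.3 refers to the Investigator's Brochure for detailed risks. A pregnant-partner instruction could sit in the consent form, and criterion 6 would make it binding. This stands. The gap is shown for the readable protocol only, and the first action must be to look.

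A second reply is that the appendix is headed as contraception guidance and may have been meant only to prevent conception. Whether semen transfer needs its own precaution is a toxicology judgement on data not shown. This also stands as a possible explanation, but it does not change what the rule permits.

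Three stronger readings are tempting, and the documents do not support them:

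- A reader might infer from Section 8.4.5 that this drug passes into semen. The text speaks of possible exposure and defines which pregnancies to follow. It reports no finding about this drug.
- A reader might infer that Sections 8.4.5 and 10.3.1 contradict each other. They do not: one follows pregnancies and the other prevents conception. The gap lies between them.
- A reader might try to size the risk from the discharge rules, which ask that at least "90% of the total dose of radioactivity administered has been recovered in urine and feces", or that no more than 1% "of the total administered radioactivity in each of 2 consecutive 24-hour intervals where both a urine and fecal sample is provided" is found. These concern radioactivity in excreta. Unrecovered radioactivity need not be retained drug, the stay "up to a maximum stay of 21 days post-dose (ie, Day 22") carries no excretion threshold, and nothing in the documents links body content to semen or foetal dose. An assumed share of men with pregnant partners would give the chance of having such a partner, not the chance of foetal exposure.

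**Conclusion.** The narrow point holds: a man whose partner is already pregnant can follow readable Section 10.3.1 exactly and take no precaution, whether or not he has had a vasectomy. It is of the lowest severity, a cheap precautionary improvement. The study gives a single 200 mg dose to about 7 men, and those who complete it stay in the unit for at least 7 days after dosing. An early withdrawer has least protection from confinement.

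The size of any foetal exposure cannot be estimated from the documents, so no figure is offered. The conclusion assumes that the consent form does not already impose the precaution and that the sponsor has no data showing semen transfer to be negligible. Either would settle the matter without an amendment. Confidence is low for that reason.

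**What to change.** 1. Check whether the consent form already requires a condom or abstinence with a pregnant partner. If it does, align Section 10.3.1 with it when the protocol is next amended.
2. If it does not, add to Section 10.3.1: *Any male participant, vasectomised or not, whose partner is pregnant must use a condom or abstain from intercourse from dosing through 90 days after dosing.*
3. Begin the vasectomy bullet with *Except with a pregnant partner,* so that it does not cancel the new sentence.
4. Put matching words in the consent form. Inclusion criterion 4 then binds participants without further change, and Section 8.4.5 can stay as it is.

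The 90 days simply match the protocol's existing window. The sponsor may shorten the period, or omit the rule, if its data support that.

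The cost is one sentence, one clause and any consent wording, with IRB/IEC approval of the amendment as Section 10.1.1 requires. It adds no visit, sample or analysis. The downside is a restriction on very few men that may prove unnecessary if transfer in semen is negligible.

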10.4 Appendix 4: Pharmacokinetic Sampling Schedule

Table 6Blood PK sampling schedule

Table 7	Urine sampling schedule

Table 8	Fecal sampling schedule
Table 8	Fecal sampling schedule

TRA, Unlabelled II	DV184001 and M12
C _{max}	Maximum observed concentration
T _{max}	Time of maximum observed concentration
AUC _{last}	Area under the concentration-time curve from time 0 to the time of the last quantifiable concentration; calculated using the linear trapezoidal rule
AUC₀₋∞	Area under the concentration-time curve from time 0 extrapolated to infinite time
AUC _{extrap(%)}	Percent of the area under the concentration-time curve due to extrapolation
λz	Terminal phase rate constant
T _{1/2}	Apparent terminal half-life
CL/F	Apparent total clearance after oral (extravascular) administration, calculated as Dose/ AUC ₀ (parent only)
Vz/F	Apparent volume of distribution during the terminal elimination phase after oral (extravascular) administration, calculated as Dose/(AUC _{0-∞} x λ_z) (parent only)
MRAUC _{0-~}	Metabolic ratio of the metabolite $AUC_{0-\infty}$ to the parent $AUC_{0-\infty}$
MRC _{max}	Metabolic ratio of the metabolite C_{max} to the parent C_{max}

Table 9 List of Whole Blood and Plasma Pharmacokinetic Parameters (non-exhaustive)

R AUC _{last} (plasma)	Ratio of unlabelled plasma study drug AUC_{last} to plasma TRA AUC_{last}		
R C _{max} (plasma)	Ratio of unlabelled plasma study drug C_{max} to plasma TRA C_{max}		

Analysis may include calculation of other PK parameters as applicable. PK calculations will be performed using WinNonlin Phoenix version 8.3.4 or higher (Pharsight Corporation).

No value for AUC_{0-∞}, λ_z , AUC_{extrap(%)}, CL/F, Vz/F, and T_{1/2} will be reported for cases that do not exhibit a terminal log-linear phase in the concentration-time profile. To the extent possible, AUC_{0-∞} values for all participants including the percentage of extrapolation will be reported.

Handling of concentrations below the limit of quantitation will be addressed in the SAP for calculations of PK parameters and for summary statistics of plasma concentrations.

Table 10 List of Urine and Feces Pharmacokinetic Parameters (non-exhaustive)

TRA	
Ae _{t1-t2}	Amount of total radioactivity excreted/recovered within a given collection interval
CumAe	Cumulative amount of total radioactivity excreted/recovered
%Dose	Percent of administered dose excreted/recovered within a given collection interval
Cum%Dose:	Cumulative percent of dose excreted/recovered
CLr	Renal clearance. $CL_r = Ae_{t1-t2}/AUC$, where both Ae_{t1-t2} and AUC are determined over matched time interval (urine only)

Analysis may include calculation of other PK parameters as applicable. PK calculations will be performed using SAS version 9.4 or higher.

10.5 Appendix 5:Toxicity Grading Scale for Healthy Adult and Adolescent Volunteers Enrolled in Preventive Vaccine Clinical Trials

Guidance for Industry

Toxicity Grading Scale for Healthy Adult and Adolescent Volunteers Enrolled in Preventive Vaccine Clinical Trials

Additional copies of this guidance are available from the Office of Communication, Training and Manufacturers Assistance (HFM-40), [name], or by calling [name] or [contact], or from the Internet at http://www.fda.gov/cber/guidelines.htm.

For questions on the content of this guidance, contact the Division of Vaccines and Related Products Applications, Office of Vaccines Research and Review at [contact].

U.S. Department of Health and Human Services

Food and Drug Administration Center for Biologics Evaluation and Research September 2007

Guidance for Industry

Toxicity Grading Scale for Healthy Adult and Adolescent Volunteers Enrolled in Preventive Vaccine Clinical Trials

This guidance represents the Food and Drug Administration's (FDA's) current thinking on this topic. It does not create or confer any rights for or on any person and does not operate to bind FDA or the public. You can use an alternative approach if the approach satisfies the requirements of the applicable statutes and regulations. If you want to discuss an alternative approach, contact the appropriate FDA staff. If you cannot identify the appropriate FDA staff, call the appropriate number listed on the title page of this guidance.

I. Introduction

Preventive vaccines are usually developed to prevent disease in a healthy population. The Office of Vaccines Research and Review, Center for Biologics Evaluation and Research, regulates preventive vaccines under authority of section 351 of the Public Health Service Act (42 U.S.C.262), as well as specific sections of the Federal Food, Drug, and Cosmetic Act, and reviews investigational new drug applications (INDs) and biologics license applications (BLAs). (See, for example, Title 21 CFR Parts 312, 600, and 601). Most of the clinical trials of preventive vaccines conducted to support INDs and BLAs enroll healthy volunteers in all phases of vaccine testing. The enrolment of healthy volunteers warrants a very low tolerance for risk in those clinical trials.

This guidance provides you, sponsors, monitors, and investigators of vaccine trials, with recommendations on assessing the severity of clinical and laboratory abnormalities in healthy adult and adolescent volunteers enrolled in clinical trials. The grading system described in the table can also be useful in defining a particular study's stopping rules (eg, a certain number of adverse events, as defined in the table, may call for stopping the study). Less extreme observations (eg, mild) may not require discontinuing the study vaccine but can still contribute to evaluating safety by identifying parameters to focus upon in subsequent product development. Uniform criteria for categorising toxicities in healthy volunteers can improve comparisons of safety data among groups within the same study and also between different studies. We, FDA, recommend using toxicity grading scale tables, provided below, as a guideline for selecting the assessment criteria to be used in a clinical trial of a preventive vaccine. We recommend incorporation of such appropriate, uniform, criteria into the investigational plan, case report forms, and study reports and correspondence with FDA, sponsors, monitors, investigators, and IRBs.

This guidance finalizes the draft guidance of the same title dated April 2005 (70 FR 22664, May 2, 2005).

FDA's guidance documents, including this guidance, do not establish legally enforceable responsibilities. Instead, guidances describe FDA's current thinking on a topic and should be viewed only as recommendations, unless specific regulatory or statutory requirements are cited. The use of the word *should* in FDA's guidances means that something is suggested or recommended, but not required.

II. Background

Standardized toxicity assessment scales have been widely used to evaluate products treating specific diseases. For example, the National Cancer Institute's Common Toxicity Criteria Scale and the Division of AIDS' Toxicity Grading Scale standardize the evaluation of adverse events among patients with cancer and HIV/AIDS, respectively (Refs. 1, 2). The defined toxicity parameters in those scales are designed for patients who may already experience mild, moderate, or severe adverse clinical or laboratory events due to the disease process, and may not be appropriate for healthy volunteers.

In the development of the toxicity grading scales for healthy volunteers, we chose parameter limit values based on published information, when such values were available (Refs. 1-6). For example, the Brighton Collaboration has developed case definitions and guidelines to evaluate some adverse events associated with administering vaccines (Ref. 3). In some cases, parameter limit values were based on clinical experience and experience reviewing vaccine clinical trials that enroll normal healthy participants.

Toxicity grading scales for laboratory abnormalities should consider the local laboratory reference values when the parameter limit values are defined. The characterisation of laboratory parameters among some populations of healthy adults and adolescents may require the exercise of clinical judgment, for example, consideration of the potential for ethnic differences in white blood cell (WBC) counts or gender differences in creatine phosphokinase (CPK) values.

III. Toxicity grading scale tables

Adverse events in a clinical trial of an investigational vaccine must be recorded and monitored and, when appropriate, reported to FDA and others involved in an investigation (sponsors, IRBs, and investigators). (See, for example, 21 CFR 312.32, 312.33, 312.50, 312.55, 312.56, 312.60, 312.62, 312.64, 312.66). Although the use of a toxicity grading scale for adverse events would not replace these regulatory requirements, using a scale to categorise adverse events observed during a clinical trial may assist you in monitoring safety and making required reports.

Nonetheless, we believe that categorisation or grading of data as outlined in this document is supplementary to and should not replace full and complete data analysis.

These guidelines for toxicity grading scales are primarily intended for healthy adult and adolescent volunteers. The parameters in the tables below are not necessarily applicable to every clinical trial of healthy volunteers. The parameters monitored should be appropriate for the specific study vaccine. For some preventive vaccines under development, it may be appropriate to include additional parameters to be monitored during a clinical trial or to alter

the choice of values in the toxicity table. For example, additional parameters might be added based on one or more of the following: safety signals observed in preclinical toxicology studies, the biological plausibility of the occurrence of certain adverse events, or previous experience with a similar licenced product.

As discussed above, the tables do not represent a recommendation to monitor all the listed parameters in all clinical trials of healthy volunteers, nor do the tables represent all possible parameters to be monitored. In addition, these tables do not represent study inclusion or exclusion criteria. We recommend that the parameters monitored be appropriate for the study vaccine administered to healthy volunteers participating in the clinical trial.

Local Reaction to Injectable Product	Mild (Grade 1)	Moderate(Grade 2)	Severe (Grade 3)	Potentially Life- Threatening (Grade 4)
Pain	Does not interfere with activity	Repeated use of non- narcotic pain reliever >24 hours or interferes with activity	Any use of narcotic pain reliever or prevents daily activity	Emergency room (ER) visit or hospitalization
Tenderness	Mild discomfort to touch	Discomfort with movement	Significant discomfort at rest	ER visit or hospitalization
Erythema/Redness *	2.5 – 5 cm	5.1 – 10 cm	>10 cm	Necrosis or exfoliative dermatitis
Induration/Swelling **	2.5 – 5 cm and does not interfere with activity	5.1 – 10 cm or interferes with activity	>10 cm or prevents daily activity	Necrosis

A. Tables for Clinical Abnormalities

* In addition to grading the measured local reaction at the greatest single diameter, the measurement should be recorded as a continuous variable.

** Induration/Swelling should be evaluated and graded using the functional scale as well as the actual measurement.
Vital Signs *	Mild (Grade 1)	Moderate(Grade 2)	Severe (Grade 3)	Potentially Life- Threatening (Grade 4)
Fever (°C) ** (°F) **	38.0 - 38.4 100.4 - 101.1	38.5 - 38.9 101.2 - 102.0	39.0 - 40 102.1 - 104	>40 >104
Tachycardia – beats per minute	101 – 115	116 - 130	>130	ER visit or hospitalization for arrhythmia
Bradycardia - beats per minute***	50 – 54	45 – 49	<45	ER visit or hospitalization for arrhythmia
Hypertension (systolic) - mm Hg	141 – 150	151 – 155	>155	ER visit or hospitalization for malignant hypertension
Hypertension (diastolic) - mm Hg	91 – 95	96 – 100	>100	ER visit or hospitalization for malignant hypertension
Hypotension (systolic) – mm Hg	85 – 89	80 - 84	<80	ER visit or hospitalization for hypotensive shock
Respiratory Rate – breaths per minute	17 – 20	21 – 25	>25	Intubation

* Participants should be at rest for all vital sign measurements.

** Oral temperature; no recent hot or cold beverages or smoking.

*** When resting heart rate is between 60 – 100 beats per minute. Use clinical judgement when characterising bradycardia among some healthy participant populations, for example, conditioned athletes.

Systemic (General)	Mild (Grade 1)	Moderate (Grade 2)	Severe (Grade 3)	Potentially Life Threatening (Grade 4)
Nausea/vomiting	No interference with activity or 1 – 2 episodes/24 hours	Some interference with activity or >2 episodes/24 hours	Prevents daily activity, requires outpatient IV hydration	ER visit or hospitalization for hypotensive shock
Diarrhea	2 – 3 loose stools or <400 gms/24 hours	4 – 5 stools or 400 – 800 gms/ 24 hours	6 or more watery stools or >800 gms/24 hours or requires outpatient IV hydration	ER visit or hospitalization
Headache	No interference with activity	Repeated use of non- narcotic pain reliever >24 hours or some interference with activity	Significant; any use of narcotic pain reliever or prevents daily activity	ER visit or hospitalization
Fatigue	No interference with activity	Some interference with activity	Significant; prevents daily activity	ER visit or hospitalization
Myalgia	No interference with activity	Some interference with activity	Significant; prevents daily activity	ER visit or hospitalization

Systemic Illness	Mild (Grade 1)	Moderate(Grade 2)	Severe (Grade 3)	Potentially Life- Threatening (Grade 4)
Illness or clinical adverse event (as defined according to applicable regulations)	No interference with activity	Some interference with activity not requiring medical intervention	Prevents daily activity and requires medical intervention	ER visit or hospitalization

B. Tables for Laboratory Abnormalities

The laboratory values provided in the tables below serve as guidelines and are dependent upon institutional normal parameters. Institutional normal reference ranges should be provided to demonstrate that they are appropriate.

Serum ¹	Mild (Grade 1)	Moderate	Severe	Potentially Life
		(Grade 2)	(Grade 3)	Threatening
				(Grade 4) ²
Sodium – Hyponatremia mEq/L	132 – 134	130 – 131	125 – 129	<125
Sodium – Hypernatremia mEq/L	144 – 145	146 - 147	148 - 150	>150
Potassium – Hyperkalemia mEq/L	5.1 – 5.2	5.3 – 5.4	5.5 – 5.6	>5.6
Potassium – Hypokalemia mEq/L	3.5 - 3.6	3.3 – 3.4	3.1 - 3.2	<3.1
Glucose – Hypoglycemia mg/dL	65 – 69	55 – 64	45 – 54	<45
Glucose –				Insulin
Hyperglycemia	100 - 110	111 – 125	>125	requirements
Fasting – mg/dL	110 – 125	126 – 200	>200	or
Random – mg/dL				hyperosmolar
				coma
Blood Urea Nitrogen	23 – 26	27 – 31	>31	Requires
(BUN) mg/dL				dialysis
Creatinine– mg/dL	1.5 – 1.7	1.8 - 2.0	2.1 - 2.5	>2.5 or requires
				dialysis
Calcium– hypocalcemia mg/dL	8.0 - 8.4	7.5 – 7.9	7.0 – 7.4	<7.0
Calcium– hypercalcemia mg/dL	10.5 – 11.0	11.1 – 11.5	11.6 - 12.0	>12.0
Magnesium –	1.3 – 1.5	1.1 – 1.2	0.9 - 1.0	<0.9
hypomagnesemia mg/dL				
Phosphorous-	2.3 – 2.5	2.0 – 2.2	1.6 – 1.9	<1.6
hypophosphatemia mg/dL				
CPK– mg/dL	1.25 – 1.5 x ULN ³	1.6 – 3.0 x ULN	3.1 –10 x ULN	>10 x ULN
Albumin– Hypoalbuminemia g/dL	2.8 - 3.1	2.5 – 2.7	<2.5	
Total Protein–	5.5 – 6.0	5.0 – 5.4	<5.0	
Hypoproteinemia g/dL				
Alkaline phosphate-	1.1 – 2.0 x ULN	2.1 – 3.0 x ULN	3.1 – 10 x ULN	>10 x ULN
increase by factor				
Liver Function Tests–ALT, AST	1.1 – 2.5 x ULN	2.6 – 5.0 x ULN	5.1 – 10 x ULN	>10 x ULN
increase by factor				
Bilirubin– when accompanied	1.1 – 1.25 x ULN	1.26 – 1.5 x ULN	1.51 – 1.75 x ULN	>1.75 x ULN
by any increase in Liver Function				
Test increase by factor				
Bilirubin– when Liver Function Test	1.1 – 1.5 x ULN	1.6 – 2.0 x ULN	2.0 – 3.0 x ULN	>3.0 x ULN
is normal; increase by factor	201 210	211 225	> 220	
	201 - 210	211-225	>226	
Pancreatic enzymes– amylase,	1.1 – 1.5 X ULN	1.6 – 2.0 X ULN	2.1 – 5.0 X ULN	>5.0 X ULN

¹ The laboratory values provided in the tables serve as guidelines and are dependent upon institutional normal parameters. Institutional normal reference ranges should be provided to demonstrate that they are appropriate.

² The clinical signs or symptoms associated with laboratory abnormalities might result in characterisation of the laboratory abnormalities as Potentially Life-Threatening (Grade 4). For example. a low sodium value that falls within a grade 3 parameter (125-129 mE/L) should be recorded as a grade 4 hyponatremia event if the participant had a new seizure associated with the low sodium value.

³ULN is the upper limit of the normal range.

Clinical Study Protocol: INDV-2000-105 Final

Hematology ¹	Mild (Grade 1)	Moderate (Grade 2)	Severe (Grade 3)	Potentially Life- Threatening (Grade 4)
Hemoglobin (Female)- gm/dL	11.0 - 12.0	9.5 - 10.9	8.0-9.4	<.0
Hemoglobin (Female) change from baseline value- gm/dL	Any decrease – 1.5	1.6 - 2.0	2.1-5.0	>.0
Hemoglobin (Male)- gm/dL	12.5 - 13.5	10.5 - 12.4	8.5 - 10.4	<8.5
Hemoglobin (Male) change from baseline value – gm/dL	Any decrease – 1.5	1.6 - 2.0	2.1 - 5.0	>5.0
WBC Increase - cell/mm ³	10,800 - 15,000	15,001 - 20,000	20,001 - 25, 000	>25,000
WBC Decrease- cell/mm ³	2,500 - 3,500	1,500 - 2,499	1,000 - 1,499	<1,000
Lymphocytes Decrease- cell/mm ³	750 – 1,000	500 - 749	250 - 499	<250
Neutrophils Decrease - cell/mm ³	1,500 - 2,000	1,000 - 1,499	500 - 999	<500
Eosinophils- cell/mm ³	650 - 1500	1501 - 5000	>5000	Hypereosinophilic
Platelets Decreased- cell/mm ³	125,000 – 140,000	100,000 - 124,000	25,000 - 99,000	<25,000
PT – increase by factor (prothrombin time)	1.0 – 1.10 x ULN ²	21.11 - 1.20 x ULN	1.21 – 1.25 x ULN	>1.25 ULN
PTT – increase by factor (partial thromboplastin time)	1.0 – 1.2 x ULN	1.21 – 1.4 x ULN	1.41 – 1.5 x ULN	>1.5 x ULN
Fibrinogen increase - mg/dL	400 - 500	501 - 600	>600	
Fibrinogen decrease - mg/dL	150 – 200	125 – 149	100 – 124	<100 or associated with gross bleeding or disseminated intravascular coagulation (DIC)

¹ The laboratory values provided in the tables serve as guidelines and are dependent upon institutional normal parameters. Institutional normal reference ranges should be provided to demonstrate that they are appropriate. ² "ULN" is the upper limit of the normal range.

Urine ¹	Mild (Grade 1)	Moderate (Grade 2)	Severe (Grade 3)	Potentially Life- Threatening (Grade 4)
Protein	Trace	1+	2+	Hospitalization or dialysis
Glucose	Trace	1+	2+	Hospitalization for hyperglycemia
Blood (microscopic) – red blood cells per high power field (rbc/hpf)	1 - 10	11-50	>50 and/or gross blood	Hospitalization or packed red blood cells (PRBC) transfusion

